CLINICAL TRIAL DOCUMENT COVER PAGE

Official Title of the Study:

Adherence to the Mediterranean Diet Following Nutritional Education and Its Effect on Anxiety, Depression, Fatigue, and Sleep Quality Among a Group of Lactating Women in Jordan: An Interventional Study

NCT Number: Not yet assigned

Document Type: Protocol / Statistical Analysis Plan

Version Number: Version 1.0

Document Date: May 2026

Sponsor / Institution: Applied Science Private University

Principal Investigator: [name]

Contact Information: [contact]

Title of the project

Adherence to the Mediterranean Diet Following Nutritional Education and Its Effect on Anxiety, Depression, Fatigue, and Sleep Quality Among a Group of Lactating Women in Jordan: An Interventional Study.

The outcome:

The aim of our study is to compare the degree of adherence to MedDiet between women who received educational and nutritional interventions during 6 months of follow-up and those without such interventions, and to examine the impact of these interventions on mothers' nutritional status, anthropometrics, and mental health.

The objectives:

The objectives of the current study are:

1. Investigate the impact of an educational intervention on MedDiet among a group of lactating women aged 18-40 years and above in Jordan over a six-month follow-up period.
2. Investigate the relationship between MedDiet adherence, obesity, and mental health. among a group of lactating women aged 18-40 years and above in Jordan over a six-month follow-up period.

Protocol**Study design and setting**

An intervention study is conducted for lactating mothers with follow-up at 3 and 6 months. Participant recruitment focuses on lactating women with infants aged 1-2 months.

The study is conducted at the Ministry of Health's childbirth vaccination clinics in Amman and Irbid, Jordan. The clinics have a fine reputation for maternal and child health services with organized working and research systems.

Ethical considerations

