Ethical approval was obtained from the Ministry of Health (MOH/REC/2024/502) and the IRB at Philadelphia University (1/1/2024-2025). The research complies with the ethical principles for medical research involving human subjects of the Helsinki Declaration. (“World Medical Association Declaration of Helsinki: Ethical Principles for Medical Research Involving Human Subjects,” 2014). All participants provide written informed consent before starting, and their right to privacy, anonymity, voluntary participation, and confidentiality are observed.

Participants

Participants consisted of eligible lactating women aged 18–40. The exclusion criteria are (1) all women aged below 18 or above 40, (2) lactating women diagnosed with mental diseases, and (3) women who were already on supplementation for managing deficiencies such as iron, B12, and vitamin D or hormonal disturbances, mainly thyroxine.

Sample size:

The sample size is calculated using 95 % confidence and an RR of 1.9, considering a 20 % non-response rate in cohorts (Rahman et al., 2007), which assumes the number of participants to be 180 based on the population of all eligible candidates who are sequentially enrolled in the study for 6 months, with an expected total research duration of 8 months.

Instruments

Validated Arabic public-domain questionnaires are distributed to collect demographic data, including age, weight, pre-pregnancy BMI, nationality, income, education, employment, insurance status, marital status, gestational age, number of children, and smoking status. Also, anthropometry and possible confounders such as physical and psychological abuse. All participants are interviewed face-to-face, and trained nutrition researchers fill out questionnaires.

A. Questionnaires:

Validated Arabic version of:

- **MEDAS:** A 14-item Mediterranean Diet Adherence Screener (14-MEDAS) is used to assess the adherence of eligible participants to MedDiet
- **Food Frequency questionnaire:** The questionnaire assesses habitual dietary intake by questioning the frequency with which food items are consumed over one week. It is adjusted in a cultural context; foods not typically used in the Jordanian diet are omitted, while foods typically used are added (Tayyem et al., 2014).

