The participants are divided into three groups. The first group receives nutritional education from a qualified nutritionist and a brochure about the Mediterranean diet. The intervention includes the importance and health benefits of MedDiet, mental health, good food sources, and lifestyle practices to maintain good nutritional status and mental health during lactation, with regular reminders about the importance of a healthy diet. These reminders are communicated through channels such as text messages or WhatsApp. The second group receives only the brochure. The brochure includes the definition and components of MedDiet, its health benefits, food sources, food alternatives rich in minerals such as iron, calcium, and B vitamins, and the importance of healthy lifestyles, including increasing physical activity and avoiding smoking. Lastly, the third group is the control group. They do not receive educational interventions or brochures. However, due to ethical considerations, the control group will receive the education and brochure after completing the study.

Statistical analysis

The database will be built in Microsoft Excel, with duplicate entries to verify data consistency. Data processing and analysis will be performed using SPSS 24 (IBM, NY, USA).

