Descriptive statistics and correlations for all quantitative and categorical study variables are calculated at baseline and at the end of the study to present the prevalence of depression, anxiety, and stress severity. Appropriate descriptive statistics such as percentages, means, and standard deviation summarize the data depending on the variable type. The Shapiro–Wilk test will be applied to assess data normality. Data are described using means (SD) and percentages. The student's t-test will be used to compare the means and medians of independent variables between groups; Pearson's Chi-Square test will be used for categorical data to test for association and probability, especially the relationship between sociodemographic variables, nutritional status, and the severity of depression, anxiety, and stress. Moreover, the significance level was set at $p < 0.05$, along with logistic regression, to identify the determinants of the severity of depression, anxiety, and stress among pregnant women attending the clinics. For the ordinal regression modeling, the severity is coded as normal = 0, mild = 1, moderate = 2, and severe = 3. The multivariable ordinal logistic regression model includes Variables statistically significant at $P \leq 0.05$ in the bivariate analyses.

References:

- Arnarson, P. Ö., Ólason, D. P., Smári, J., & Sigurdsson, J. F. (2008). The Beck Depression Inventory Second Edition (BDI-II): Psychometric properties in Icelandic student and patient populations. *Nordic Journal of Psychiatry*, 62(5), 360–365. <https://doi.org/10.1080/08039480801962681>

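### The plan does not say which women are in the baseline and end-of-study severity prevalences, and names no repeated-measures method, so drop-out related to mood could shift the apparent change in either direction

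*Combined protocol and SAP*

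**What the plan says.** All references are to the combined protocol and SAP.

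- **Statistical analysis.** Descriptive summaries "are calculated at baseline and at the end of the study to present the prevalence of depression, anxiety, and stress severity". No analysis set or denominator is given for either time. The methods named are Student's t-test between groups, Pearson's chi-square test, and logistic and ordinal regression. For the ordinal model, "the severity is coded as normal = 0, mild = 1, moderate = 2, and severe = 3". No paired or repeated-measures method is named, and there is no rule on missing data, drop-outs or completers anywhere in the document.
- **Sample size.** The calculation is made "considering a 20 % non-response rate in cohorts", "which assumes the number of participants to be 180". The text does not say whether non-response means refusal at entry, loss during follow-up, or both.
- **Study design and setting.** "An intervention study is conducted for lactating mothers with follow-up at 3 and 6 months". The sentence on prevalence does not use the 3-month visit.
- **Educational Intervention.** "The participants are divided into three groups": education plus brochure, brochure only, and control. The allocation ratio is not stated.
- **Instruments.** Questionnaires are completed by researchers in face-to-face interviews. The schedule of instruments by visit is not given, and no procedure is described for a woman who misses a visit.

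**The concern.** Mental health over six months is part of the stated aim, and the two prevalences are the only display of it over time that the plan spells out. Readers may well take the difference between them as the change during the programme.

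That reading is sound only if both figures come from the same women, or if those lost resemble those who stay. The plan secures neither. Someone following it literally with available data would put every enrolled woman in the first figure and only those still attending in the second. If mothers with worse mood are more likely to stop attending, prevalence falls although no woman has improved. If they are more likely to stay, it rises. Nothing in the plan would show which had happened. If the pattern also differed by group, for example because one group receives regular reminders and the control group does not, the distortion would enter the comparison between groups.

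**Working it through.** **Inputs from the plan.** 180 women, a 20% allowance for non-response, and three groups.

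**The plan's own figure.** The total of 180 cannot be tied to one calculation, because power and baseline risk are not stated. It can be reached under assumed inputs: three groups, RR 1.9, 90% power, two-sided 5% level and a baseline risk of 0.36 give 48 per group; 48/0.8 = 60, and 3 × 60 = 180. The point here does not depend on this. The total of 180 is taken as the number enrolled.

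**Assumptions.** The 20% is taken as loss by 6 months. A case is a woman with moderate or worse severity. Baseline prevalence is p, no woman's status changes, and cases drop out r times as often as non-cases. The documents give neither p nor r.

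**Formulae.** With overall loss L:

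- drop-out in non-cases: d0 = L / (p·r + 1 − p)
- drop-out in cases: d1 = r·d0
- prevalence among women still present: p(1 − d1) / (1 − L)

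**Worked example, p = 0.30, L = 0.20.** Lost: 180 × 0.20 = 36. Remaining: 144. Cases at baseline: 54.

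- r = 2: d0 = 0.20/1.30 = 0.154 and d1 = 0.308. Cases lost 16.6, cases remaining 37.4. 37.4/144 = 26.0%, a shift of −4.0 points.
- r = 1: cases remaining 54 × 0.80 = 43.2. 43.2/144 = 30.0%, no shift.
- r = 0.5: d0 = 0.20/0.85 = 0.235 and d1 = 0.118. Cases remaining 47.6. 47.6/144 = 33.1%, a shift of +3.1 points.

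**Range at 20% loss (shift in percentage points, no true change):**

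| Baseline prevalence | r = 0.5 | r = 1 | r = 1.5 | r = 2 | r = 3 |
|---|---|---|---|---|---|
| 20% | +2.2 | 0 | −1.8 | −3.3 | −5.7 |
| 30% | +3.1 | 0 | −2.3 | −4.0 | −6.6 |
| 40% | +3.8 | 0 | −2.5 | −4.3 | −6.7 |
| 50% | +4.2 | 0 | −2.5 | −4.2 | −6.3 |

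The outer limits at 30% baseline are (54 − 36)/144 = 12.5% if every woman lost is a case, and 54/144 = 37.5% if none is.

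**If loss is smaller.** With L = 0.10, p = 0.30 and r = 2: d0 = 0.10/1.30 = 0.077 and d1 = 0.154. Cases remaining 54 × 0.846 = 45.7, out of 162, which is 28.2%, a shift of −1.8 points. With no loss the shift is 0.

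**Same women at both times.** In the r = 2 example, the 144 retained women had 37.4 cases at baseline and have 37.4 at the end. The figure is 26.0% both times, so the artefact is exactly 0.

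**Between groups.** Assume equal groups of 60 with 18 cases each and 48 remaining. If r = 2 in every group, each ends at 26.0% and the difference is 0. If r = 2 in one group and r = 1 in another, the first ends at 18 × 0.692/48 = 26.0% and the second at 18 × 0.80/48 = 30.0%, a difference of 4.0 points with no true effect.

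**The case against.** The strongest reply is that the plan is silent rather than wrong. A table of completers at both times would fit the sentence just as well. The sentence is descriptive, no before-after test is specified, and the stated aim is a comparison between groups, where similar drop-out would largely cancel. All of this stands.

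It also limits what may be concluded. A reader might infer any of the following, and the documents support none of them:

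- **That the plan prescribes all enrolled women at baseline and only the remaining women at the end.** It states no denominator. The mismatch is what follows if available data are used.
- **That the plan expects 20% loss to follow-up.** It speaks of non-response, which could cover refusal at entry.
- **That a woman who misses the visit has no end-of-study value.** This is plausible given face-to-face interviews, but other contact is not ruled out.
- **That drop-out will look like improvement.** The documents give no drop-out rate by mood. The shift can be zero or an apparent worsening. Women with diagnosed mental disease are excluded, which also bears on the prevalence to be assumed.
- **That the group comparison is biased.** That requires the pattern of drop-out to differ by group.

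Two practical objections also stand. A same-women table describes completers only, so it removes the changing denominator but not the selection. A table of women lost against retained would rest on about 36/3 = 12 lost women per group at 20% loss and equal groups, too few for firm conclusions.

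None of this supplies the missing definition or a method that uses the repeated measurements.

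**Conclusion.** The point holds as an omission that is cheap to repair. The plan leaves the women in each prevalence undefined and names no method that links a woman's values over time.

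At 20% loss, no true change, baseline prevalence of 20% to 50% and cases dropping out half to three times as often as non-cases, the artefact runs from +4.2 to −6.7 points, and it is 0 when drop-out is unrelated to mood. Loss, prevalence and drop-out ratio are all assumptions, and the shift shrinks with smaller loss. The comparison between groups is affected only by differential drop-out: 4.0 points in the example shown. The documents do not allow the direction to be predicted.

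**What to change.** Amend the Statistical analysis section as follows.

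1. Report severity prevalence by assigned group at baseline, 3 months and 6 months, each with its denominator.
2. Base any statement of change on the same women at both times, and label it as a completers' result.
3. Make the main between-group comparison of DASS-21 and the other scores a likelihood-based repeated-measures (mixed) model by group, using baseline and all available 3- and 6-month values, in place of t-tests on the women present at the end. The model can allow for drop-out related to scores already observed, but not for drop-out that depends on mood never recorded. State that limit.
4. Tabulate baseline scores of women lost and retained in each group, as description only and without tests.
5. Under Sample size, say whether the 20% is refusal at entry, loss to follow-up, or both.

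The cost is modest extra analysis work and no new visits. Use of month-3 data assumes that the instruments are given at that visit, so the plan should state the schedule of instruments by visit.

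### Three groups are followed to months 3 and 6, but the only stated comparison of means is a two-group t-test with no baseline adjustment, no choice of contrast and no use of month 3

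*Combined protocol and SAP*

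**What the plan says.** Under Study design and setting: "An intervention study is conducted for lactating mothers with follow-up at 3 and 6 months". Under B. Educational Intervention: "The participants are divided into three groups". One group receives education, a brochure and reminders; one receives the brochure alone; the control group receives neither until the study is over. The text gives no allocation method or ratio.

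Under Statistical analysis, the sentence on comparing means is: "The student's t-test will be used to compare the means and medians of independent variables between groups". The threshold follows: "the significance level was set at $p < 0.05". The only time points mentioned there are in the descriptive sentence: "Descriptive statistics and correlations for all quantitative and categorical study variables are calculated at baseline and at the end of the study".

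The section also plans chi-square tests for categorical data and a logistic or ordinal regression. The stated purpose of the regression is "to identify the determinants of the severity of depression, anxiety, and stress among pregnant women attending the clinics", and its covariates are chosen by significance in bivariate tests.

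**The concern.** The stated aim is to compare diet adherence between women who did and did not receive the interventions, and to examine the effect on nutritional status, anthropometrics and mental health. For the continuous outcomes (MEDAS, DASS-21, MFIS, PSQI, BDI, SF-36, BMI), the t-test is the only stated route to that comparison. It does not fit the design in four ways.

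- **Groups.** A t-test takes two groups and the trial has three. Someone must later choose between all three pairs, the two comparisons with control, one pair, or the two active groups pooled. The plan makes no choice, so it can be made after the results are seen.
- **Baseline.** Study variables are summarised at baseline, so the scores will exist, but no group comparison uses them.
- **Month 3.** It is a scheduled visit with no stated analysis.
- **Form.** A t-test does not compare medians, and nothing is offered if the Shapiro–Wilk test rejects normality.

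At stake are the false-positive rate of the main comparison and the precision of the estimated effect. Because allocation is not described, measured baseline imbalance may also be left in the estimate.

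**Working it through.** The plan gives no power or error rate for this comparison, so there is no figure of its own to reproduce. Its total of 180 cannot be checked either, because power and baseline risk are not stated.

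**Inputs from the documents.** Three groups; follow-up at months 3 and 6; a 0.05 threshold; 180 women; a 20% non-response allowance (Sample size).

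**Assumptions.** Two-sided tests; equal groups; common variance; a true difference of 0.5 SD; a baseline-to-follow-up correlation ρ of 0.3, 0.5 or 0.7. None of these is in the documents. Group size is 180 / 3 = 60, or 180 × 0.8 / 3 = 48 if the 20% is treated as loss after enrolment.

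**1. False positives, one outcome at one visit, no true differences.** Three independent tests would give 1 − 0.95³ = 14.3%. The pairs share groups, so the actual figure is lower. Simulation of 400,000 trials gives:

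| Rule | 60 per group | 48 per group |
|---|---|---|
| All three pairs at 0.05 | 12.1% | 12.3% |
| Two comparisons with control at 0.05 | 9.0% | 9.1% |
| Pairs tested only after a significant three-group F-test | 5.0% | 5.0% |
| All three pairs, Bonferroni 0.05/3 | 4.4% | 4.4% |

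A single pre-chosen pair, or one pooled test, stays at 5%.

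**2. Precision lost by omitting baseline.** Adjustment multiplies the variance by 1 − ρ²: 0.91, 0.75 and 0.51 for ρ = 0.3, 0.5 and 0.7. By normal approximation, power = Φ(0.5 / √(2(1 − ρ²)/n) − 1.96).

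Example with n = 48:
- Unadjusted: 0.5 / √(2/48) = 2.449, and Φ(2.449 − 1.96) = 69%.
- ρ = 0.5: 2.449 / √0.75 = 2.828, and Φ(2.828 − 1.96) = 81%.

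| n per group | Unadjusted | ρ = 0.3 | ρ = 0.5 | ρ = 0.7 |
|---|---|---|---|---|
| 48 | 69% | 73% | 81% | 93% |
| 60 | 78% | 82% | 89% | 97% |

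**3. Whether another stated method fills the gap.** Chi-square is for categorical data. The regression models DASS severity categories and looks for determinants; group, visit and baseline score are not named as terms. Neither estimates the group effect on a continuous score.

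**4. Whether ordering the contrasts is enough.** Nine continuous outcomes (MEDAS, three DASS-21 subscales, MFIS, PSQI, BDI, SF-36 counted once, BMI), each held at 5%, would give up to 1 − 0.95⁹ = 37% if independent. Ordering within each outcome does not control this, so a primary outcome is also needed.

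**The case against.** The strongest reply is that the plan does not say what it is being faulted for. The t-test sentence refers to independent variables and names no outcome, visit or pair of groups. The aim is phrased two ways, intervention against none, so a single pooled test is a fair reading, and that test has 5% error. This stands as a limit on the claim: the plan leaves the comparison open and does not commit to three uncorrected pairwise tests. It does not remove the gap, because no stated method handles three groups, baseline or month 3.

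Three stronger readings are tempting, and the documents support none of them.

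- **That without baseline and repeated measures the effect cannot be told apart from postpartum recovery.** Recovery common to all groups cancels in any concurrent between-group comparison, including a plain t-test at month 6. Baseline adjustment adds precision and deals with measured imbalance. Repeated measures add information and help with missing visits.
- **That pooling the two active groups must cost power.** This depends on the unknown brochure effect. Take 48 per group and an education effect of 0.5 SD. The pooled standard error is √(1/96 + 1/48) = 0.177 SD. A brochure effect of 0.25 SD gives a pooled contrast of 0.375 SD and 56% power; a brochure effect of 0.5 SD gives 81%. Education against control alone gives 69%, so pooling can lose or gain.
- **That the plan expects to lose 20% of women during follow-up.** The Sample size section speaks of non-response, not attrition. This is why results are shown at both 48 and 60 per group.

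It is also fair to say that a mixed model is not the only remedy. Analysis of covariance at month 6 with a gated three-group test would also control error within an outcome, but it would leave month 3 unused.

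**Conclusion.** The point holds in this form: the stated method for group means is a two-group test applied to a three-group, two-follow-up design, with no baseline term, contrast rule or month-3 analysis. That it would be applied to follow-up scores is an inference, made because nothing else in the plan covers them.

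The size is conditional. Error is about 12% per outcome and visit only if all three pairs are tested ungated, and it is lower under the other readings. The inflation comes from repeated testing, not from leaving out baseline. The cost of leaving out baseline is mainly precision: between 4 and 24 percentage points of power at 48 per group (69% to 73% or 93%), and between 4 and 19 at 60 (78% to 82% or 97%), under the assumed 0.5 SD difference and correlations. Since participants are described only as divided into groups, adjustment would also reduce bias from measured baseline imbalance. It would not remove confounding if allocation is not random.

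This should be settled before any between-group analysis is run.

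**What to change.** Replace the t-test sentence under Statistical analysis with:

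> The primary outcome is the MEDAS score at 6 months. Each continuous outcome at 3 and 6 months will be analysed with a linear mixed model for repeated measures with group (3 levels), visit, group × visit, baseline score, baseline × visit and city (Amman or Irbid), and unstructured within-woman covariance, with all women analysed in the group to which they were assigned. For the primary outcome the 6-month contrasts are tested in fixed order at two-sided 0.05: education versus control, brochure versus control, education versus brochure. All other outcomes are secondary and reported with 95% confidence intervals without confirmatory claims.

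MEDAS is proposed because adherence is the first comparison named in the aim, and city because clinics in both cities take part. The sponsor should confirm both the primary outcome and the order of contrasts before seeing results by group. The ordinal severity model can stay as a separate analysis of determinants.

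The cost is a change of wording and slightly more analysis work in the software already named, with no new data or participants. The fixed order has a price: if education versus control is not significant, the later contrasts cannot be claimed as confirmed.

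### Student's t-test is the only test named for means, and nothing in the plan secures equal group sizes; Welch's form would protect against unequal spread at almost no cost

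*Combined protocol and SAP*

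**What the plan says.** The Statistical analysis section of the combined protocol and SAP states that Student's "t-test will be used to compare the means and medians of independent variables between groups". It gives no unequal-variance form, no check on variances and no alternative test for means.

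On group sizes:

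- Under B. Educational Intervention, "The participants are divided into three groups": education plus brochure, brochure only, and control. No allocation ratio or per-group number is given.
- Under Sample size there is only a total, "which assumes the number of participants to be 180", and an allowance, "considering a 20 % non-response rate in cohorts".
- Under The outcome, the aim is a contrast "between women who received educational and nutritional interventions during 6 months of follow-up and those without such interventions". The text does not say which of the three groups form each side.

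**The concern.** The equal-variance t-test estimates one common variance from both groups. When group sizes and SDs both differ, that estimate is weighted towards the larger group, and the standard error of the difference is wrong. If the smaller group is the more variable, the standard error is too small and the test rejects too often. If the larger group is the more variable, the standard error is too large and power is lost.

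The plan leaves room for unequal sizes in three ways. Arm sizes are unstated and may be changed further by uneven loss. The aim could be read as two active groups against one control. The t-test is also assigned to independent variables in general, which may involve groups whose sizes nobody controls. At stake is whether a reported p value just under or over 0.05 means what it says.

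**Working it through.** **1. Inputs.** From the documents: 180 women, three groups, 20% non-response, significance at 0.05. Assumed, because the documents are silent: a two-sided test, equal thirds (180/3 = 60 per arm), loss applied per arm (60 × 0.8 = 48), normally distributed scores, and one SD 1.25 or 1.5 times the other.

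**2. The plan's own figure.** The total of 180 cannot be reproduced from what is stated: "The sample size is calculated using 95 % confidence and an RR of 1.9" gives neither power nor baseline risk. It can be approached under assumptions. Two groups, 80% power and risks of 0.25 v 0.475 (0.25 × 1.9) need 71 per group, or 142 in all, and 142/0.8 = 177.5, rounded up to 178. This calculation fixes no arm sizes, so it does not settle the present point.

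**3. Formulae.**

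- Variance of the difference that the equal-variance test uses, on average: s² × (1/n1 + 1/n2), with s² = [(n1 − 1)σ1² + (n2 − 1)σ2²] / (n1 + n2 − 2).
- True variance of the difference: σ1²/n1 + σ2²/n2.
- If n1 = n2 = n, both equal (σ1² + σ2²)/n. The standard error is then right whatever the SDs, and only the degrees of freedom differ from Welch's.

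**4. Numbers at SD ratio 1.5** (the smaller SD set to 1).

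60 v 48, where one arm loses 20% and the other nobody:

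- Smaller group more variable: s² = (59 × 1 + 47 × 2.25)/106 = 1.554. Variance used: 1.554 × 0.0375 = 0.0583. True: 1/60 + 2.25/48 = 0.0635. Standard error ratio √(0.0583/0.0635) = 0.96.
- Larger group more variable: s² = (59 × 2.25 + 47 × 1)/106 = 1.696. Variance used: 0.0636. True: 2.25/60 + 1/48 = 0.0583. Ratio 1.04.

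96 v 48, where two active groups of 48 are merged against one control of 48:

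- Smaller group more variable: s² = (95 × 1 + 47 × 2.25)/142 = 1.414. Variance used: 1.414 × 0.03125 = 0.0442. True: 1/96 + 2.25/48 = 0.0573. Ratio 0.88.
- Larger group more variable: s² = (95 × 2.25 + 47 × 1)/142 = 1.836. Variance used: 0.0574. True: 2.25/96 + 1/48 = 0.0443. Ratio 1.14.

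**5. Resulting error rates.** Simulated under equal means, normal data, two-sided 5%:

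| Sizes | SD ratio | Equal-variance test, smaller group more variable | Equal-variance test, larger group more variable | Welch |
|---|---|---|---|---|
| 48 v 48 | 1.25 to 1.5 | 5.0–5.1% | 5.0–5.1% | 5.0% |
| 60 v 48 | 1.25 | 5.6% | 4.4% | 5.0% |
| 60 v 48 | 1.5 | 6.1% | 4.1% | 5.0% |
| 96 v 48 | 1.25 | 6.9% | 3.5% | 5.0% |
| 96 v 48 | 1.5 | 8.5% | 2.6% | 5.0% |

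Repeated simulations differ by about 0.1 points.

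**6. Power.** At 96 v 48, with the larger group 1.5 times as variable and a true difference of 0.6 of the smaller SD, power is about 73% for the equal-variance test and 81% for Welch. With equal variances and power near 80%, Welch gives up about 0.3 points (79.9% v 80.2%).

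**The case against.** The strongest reply is that the documents do not establish the conditions under which the test fails. Most of that reply stands.

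- **Unequal arms.** A reader might infer that the groups are unequal by design. No section states an unequal split. The natural default is equal thirds, and there the two tests agree.
- **Merged active groups.** A reader might infer a 2:1 comparison from the aim. The plan never says that the active groups are combined. The aim fits education plus brochure against control equally well, and the second group receives only a brochure. The 96 v 48 figures are therefore conditional on a choice that the plan has not made.
- **Subgroup comparisons and model entry.** A reader might infer that specific subgroup t-tests are planned and that their p values decide which variables enter the ordinal model. The section does say "The multivariable ordinal logistic regression model includes Variables statistically significant at" P ≤ 0.05 in bivariate analyses. But it directs the relationship between sociodemographic variables, nutritional status and severity chiefly to the chi-square test, and severity has four levels. The t-test's part in that screen is not established.
- **Spread.** No SDs are given, so the ratios are assumptions. If spread changes only because the intervention works, the null hypothesis is false, and the effect falls on power rather than on false positives.
- **Form of the test.** The equal-variance form is read from the test's name. That is the ordinary reading, but the section does not spell it out.

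What the reply does not show is that sizes will be equal. With no stated allocation and 20% non-response expected, the plan offers no such assurance. Nor does the reply identify a cost that would argue against Welch.

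**Conclusion.** The point holds as a conditional improvement, not as a demonstrated error. If both sizes and SDs differ, with an SD ratio of 1.25 to 1.5 and normal scores, the nominal 5% test runs at about 4.1% to 6.1% for 60 v 48. Uneven loss could produce that split, although it takes the whole 20% falling on one arm. At 96 v 48 it runs at about 2.6% to 8.5%, and only if the active groups are merged. At equal sizes nothing changes. It would go too far to say that the planned p values are wrong: the documents neither give nor rule out the unequal sizes and spreads that this would need. The priority is optional.

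**What to change.** In the Statistical analysis section, replace Student's t-test with Welch's unequal-variance t-test for any two-group comparison of means, and say that no preliminary test of variances will be used to choose between them. The cost is one phrase, no new data, and about 0.3 points of power if variances are in fact equal.

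This does not repair the separate problems in the same section: a two-group test in a three-group study, no method for the visits at 3 and 6 months, and a t-test said to compare medians. Those need their own changes.
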